### 13 Demographics and Other Baseline Characteristics

Demographic data and other baseline characteristics will be presented using summary statistics for continuous variables and frequency tables for categorical variables.

### 13.1 Demographics

Demographic characteristics will be summarized overall and by treatment sequence for each group using the following information from the Screening/Baseline Visit CRF pages.

Demographic characteristics:

- Sex: Male, Female
- Race: Chinese, Non-Chinese
- Age (years): summary statistics
- Weight (kg): summary statistics
- Height (cm): summary statistics
- BMI (kg/m^2): summary statistics

Specifications for computation.

Age [years]:

- (date of given informed consent date of birth + 1) / 365.25
- In case of missing date that according to section 11: day will be imputed as 15 if it is missing, and month imputed as June if missing. If both of day and month are missing, they will be imputed as July 1st. If year is missing then the date will not be imputed.

## 13.2 Medical History

The medical history will be summarized from the "Medical History" eCRF page, using MedDRA, version 20.0, preferred term as event category and MedDRA system organ class (SOC) body term as Body System category.

Medical history will be displayed in terms of frequency tables overall and by treatment sequence for each group: ordered by primary SOC and PT in alphabetical order.

#### 13.3 Other Baseline Characteristics

The following baseline characteristics will be summarized overall and by treatment sequence for each group:

- Nicotine and Alcohol Consumption
- Urine screening of drugs of abuse
- Breath test of alcohol

Baseline characteristics with respect to vital signs, physical examinations, ECG recordings, and laboratory tests will describe in Section 17

Results of chest x-ray and serum pregnancy test (for women of childbearing potential) will be listed only.

#### 14 Previous or Concomitant Medications/Procedures

All previous or concomitant medications will be coded by the most current WHODrug (enhanced) 01Mar2017.

Missing or partial dates for medications will not be imputed. In the case where it is not possible to define a medication as prior or concomitant, the event will be classified by the worst case; i.e. prior and concomitant.

**Previous medications** are medications taken prior to screening visit, other than trial medications and pre-medications for trial drug, which started and ended before first administration of trial drug. Prior medications within 1 month before screening will be collected.

Concomitant treatments are medications, other than trial medications, which are taken by subjects any time on-trial (include medications which started before the first trial drug treatment and were ongoing after first trial drug treatment, or started on or after the first day of trial drug treatment).

Previous and concomitant medications/procedures will be summarized overall for both groups as well as overall and by treatment sequence for each group, and by PT and ATC 2nd level, respectively. The listing of previous and concomitant medications/procedures will be generated.

## 15 Treatment Compliance and Exposure

Study drug administration will be listed by group, treatment sequence and subject with treatment, date and time of administration.

## 16 Endpoint Evaluation

## 16.1 Primary Endpoint Analyses

The primary endpoints are the following PK parameters calculated from bisoprolol and amlodipine plasma concentrations:

- AUC0-t of bisoprolol
- Cmax of bisoprolol
- AUC0-t of amlodipine
- Cmax of amlodipine

groups

The null and alternative hypotheses are as follows:

```
\begin{split} H_0: & \textit{for AUC}_{0-t} \ \ \mu_T \ / \ \mu_C \leq 0.8 \ \textit{or} \ \mu_T \ / \ \mu_C \geq 1.25 \\ & \textit{for C}_{\max} \ \ \mu_T \ / \ \mu_C \leq 0.8 \ \textit{or} \ \mu_T \ / \ \mu_C \geq 1.25 \end{split}, \text{ for at least 1 primary endpoint} \\ H_1: & \textit{for AUC}_{0-t} \ \ 0.8 < \mu_T \ / \ \mu_C < 1.25 \\ & \textit{for C}_{\max} \ \ \ 0.8 < \mu_T \ / \ \mu_C < 1.25 \end{split}, \text{ for all 4 primary endpoints and for both fasting and fed} \end{split}
```

where  $\mu_T$  and  $\mu_C$  are the geometric means of the primary endpoints following investigational product (Treatment A) and comparators (Treatment B), respectively.

The analysis of primary endpoints will be based on the PK Population (Section 10.2)

The primary endpoints, Cmax and AUC0-t in fasting or fed group, will be log-transformed and a mixed-effects model will be applied. The model will include fixed effects for sequence, treatment, and period and a random effect of subject nested within sequence. Treatment differences on the log scale will be estimated for the parameters together with their 90% CIs. The least squares means together with their 95% CIs by treatment will also be estimated. Point estimates and CIs will be back-transformed to the original scale for presentation, i.e., ratios of geometric means and corresponding 90% CIs for Treatment A/Treatment B, geometric means and corresponding 95% CIs by treatment, respectively. Intra-subject CV estimated from the model will also be presented. The BE will be established if all 4 sets of the 90% CIs for the ratios of geometric means between the investigational product and the comparators fall within 80.00% to 125.00%.

The following example code could be used:

```
proc mixed data=pkparam;
by food analyte param;
class sequence period trt subjid;
model lnest = sequence period trt /ddfm=kr;
random subjid(sequence);
estimate 'A vs B' trt 1 -1 /alpha=0.1 cl;
lsmeans trt /alpha=0.05 cl;
```

#### run;

All primary PK endpoints will be descriptively summarized as described in Section Error! Reference source not found. Graphs of individual values and geometric mean will be presented for primary PK parameters versus treatment and food condition. Boxplots will also be created for primary PK parameters versus group and treatment.

## 16.2 Secondary Endpoint Analyses

All secondary PK endpoints will be descriptively summarized as described in Section 11. The secondary PK endpoints are the following parameters in plasma for bisoprolol and amlodipine:

•  $t_{max}$ ,  $t_{1/2}$ ,  $\lambda_Z$ ,  $AUC_{0-\infty}$ ,  $AUC_{extra}$ %, CL/f,  $V_{z/f}$ .

For  $t_{max}$ , the Hodges-Lehmann estimates for the treatment differences and corresponding 90% CIs according to the Tukey method will be calculated.

The mixed-effects model for treatment comparison as described for the primary endpoints will also be applied to  $AUC_{0-\infty}$ . The ratios of geometric means and corresponding 90% CIs for Treatment A/Treatment B will be estimated.

All secondary endpoints ( $t_{max}$ ,  $t_{1/2}$ ,  $\lambda_Z$ ,  $AUC_{0-\infty}$ ,  $AUC_{extra\%}$ , CL/f, and  $V_{z/f}$ ) will be summarized descriptively by group and treatment on the PK analysis set.

## 16.3 Other Endpoint Analyses

## 16.3.1 Analysis on PK / Population PK Endpoints

Pre-dose samples that occur before the first drug administration will be assigned a time of 0 hours, as if the sample had been taken simultaneously with the study drug administration.

Pharmacokinetic concentrations which are erroneous due to a protocol deviation (as defined in the protocol), documented handling error or analytical error (as documented in the bioanalytical report) may be excluded from the PK analysis if agreed upon prior to performing a statistical analysis. In this case the rationale for exclusion must be provided in the Clinical Trial Report (CTR). Any other PK concentrations that appear implausible to the Pharmacokineticist/PKPD Data Analyst must not be excluded from the analysis. Any implausible data will be documented in the CTR.

Plasma concentration data will be summarized descriptively for bisoprolol and amlodipine as described in Section 11. Values below the lower limit of quantification (LLOQ) will be taken as zero for descriptive statistics of PK concentrations. Missing concentrations (e.g., no sample, insufficient sample volume for analysis, no result, or result not valid) will be reported and displayed generally as "N.R.".

## Bisoprolol Amlodipine 5 mg/5 mg Combination Tablets EMR200006-001

Two-period Crossover Bioequivalence Final Version 2.2

Samples that are collected outside the specified time windows will be included in the PK analysis but excluded from the concentration summary. The PK sampling collection schedule is presented in Table 1 below.

Table 1 Pharmacokinetic Sample Collection Schedule

Trial Day	Period Day	Time of Blood Sample (hour)	Window Allowance (minute)
1	1 - Predose in Period 1	Baseline blood draw (10 minutes prior to drug administration)	±2
1	1 – Single dose administration and Washout begins	0.5, 1, 1.5, 2, 3, 4, 6, 8, 10, 12, 15	±2
2	2	24, 36	±5
3	3	48	±5
4	4	72	±30
5	5	96	±30
6	6	120	±30
7	7	144	±30
8	8	168	±30
9 - 14			
15	1-Predose in Period 2	Baseline blood draw (10 minutes prior to drug administration)	±2
15	1- Single dose administration and Washout begins	0.5, 1, 1.5, 2, 3, 4, 6, 8, 10, 12, 15	±2
16	2	24, 36	±5
17	3	48	±5
18	4	72	±30
19	5	96	±30
20	6	120	±30
21	7	144	±30
22	8	168	±30
23 - 28			
End of Trial (Day 29)/Premature Withdrawal		1-sample	±30

Arithmetic mean plasma bisoprolol and amlodipine concentration versus scheduled (nominal) time plots will be provided for each treatment and food condition using a linear and semi-logarithmic scale. Mean plots will include SD error bars ( $\pm$ SD) when plotted on a linear scale. The mean plasma concentration-time profiles will be plotted for subjects included in the respective PK Analysis Set.

Individual plasma bisoprolol and amlodipine concentration versus actual time plots will be provided for each treatment by food condition using a linear and semi-logarithmic scale. Plots of individual profiles of plasma bisoprolol and amlodipine concentration versus actual time for all subjects within each treatment, presented on a single plot (i.e., spaghetti plots), will be provided by Fed/Fasting group, separately, using a linear and semi-logarithmic scale. All statistical analyses and descriptive summaries of PK data will be performed on the PK Analysis Set. Pharmacokinetic concentrations will be listed for all subjects by treatment and group; concentrations excluded from the PK analysis will be flagged within the listing

A listing of PK blood sample collection times by individual, as well as derived sampling time and time deviations, will be provided.

# 16.3.2 Estimation of Individual Pharmacokinetic Parameters by Noncompartmental Analysis

For the PK analysis, predose sample concentrations that are missing will be assigned a numerical value of zero for the calculation of AUC. Any anomalous concentration values observed at predose will be identified in the CTR, and if the anomalous predose concentration value is greater than 5.00% of the  $C_{max}$  in the profile, the profile will be excluded from summaries and inferential statistics as appropriate; handling of the data will be documented in the CTR. Pharmacokinetic parameters for the affected profile shall be calculated as part of the WinNonlin® run and will be listed.

Pharmacokinetic parameters will be calculated using standard non-compartmental methods. Pharmacokinetic parameters will be evaluated and listed for all volunteers who provide sufficient concentration-time data. At least 3 valid, postdose concentration points will be required in the PK profile to obtain any PK parameter estimate.

Pharmacokinetic parameters will be calculated using the actual elapsed time since dosing, given with a precision of 14 significant digits or the SAS format Best12. In cases where the actual sampling time is missing, calculations will be performed using the scheduled time. Otherwise, there will be no further imputation of missing data other than for a missing predose concentration as stated above.

For each subject in the PK Analysis Set the following PK parameters will be calculated for bisoprolol and amlodipine, where appropriate:

Symbol	Definition
AUC 0-t	The area under the concentration-time curve (AUC) from time zero (= dosing time) to the last sampling time ( $t_{last}$ ) at which the concentration is at or above the LLOQ. Calculated using the mixed log linear trapezoidal rule (linear up, log down). Units: $ng*h/mL$ .

Symbol	Definition
AUC 0 -∞	The AUC from time zero (dosing time) extrapolated to infinity, based on the predicted value for the concentration at $t_{last}$ , as estimated using the linear regression from $\lambda_z$ determination. $AUC_{0-\infty} = AUC_{0-t} + C_{last  pred} / \lambda_z$ . Units: $ng*h/mL$ .
AUC extra %	The AUC from time $t_{last}$ extrapolated to infinity given as percentage of $AUC_{0-\infty}$ . $AUC_{extra\%} = (extrapolated area/AUC_{0-\infty})*100$ . The predicted $AUC_{0-\infty}$ should be used. Units: %.
CL/f	The apparent total body clearance of drug following extravascular administration. $CL/f = Dose_{p.o.}/AUC_{0-\infty}$ . The predicted $AUC_{0-\infty}$ should be used. The dose amounts to be used for this calculation are 5 mg for bisoprolol and 5 mg for amlodipine. Units: $L/h$ .
C max	Maximum observed concentration, taken directly from the observed concentration-time profile. Units: ng/mL.
$t_{max}$	The time to reach the maximum observed concentration collected during a dosing interval (unless otherwise defined, take the first occurrence in case of multiple/identical $C_{max}$ values). Units: h.
t 1/2	Apparent terminal half-life. $t_{1/2} = \ln (2)/\lambda_z$ . Units: h.
$V_{z/f}$	The apparent volume of distribution during the terminal phase following extravascular administration $V_{z/f} = Dose/(AUC_{0-\infty}*\lambda_z)$ following single dose. Units: L.
$\lambda_z$	Terminal elimination rate constant. Determined from the terminal slope of the log-transformed concentration curve using linear regression on terminal data points of the curve. Units: h  .

The following PK parameters will be calculated for diagnostic purposes and listed, but will not be summarized:

- The time interval (h) of the log-linear regression ( $\lambda_{z \text{ lower}}$ ,  $\lambda_{z \text{ upper}}$ ) to determine  $\lambda_{z}$ .
- Number of data points  $(N_{\lambda})$  included in the log-linear regression analysis to determine  $\lambda_z$ .
- Goodness-of-fit statistic (Rsq) for calculation of  $\lambda_z$ .

The regression analysis should contain data from at least 3 different time points in the terminal phase consistent with the assessment of a straight line on the log-transformed scale. Phoenix WinNonlin best fit methodology will be used as standard. The last quantifiable concentration should always be included in the regression analysis, while the concentration at tmax and any concentrations <LLOQ which occur after the last quantifiable data point should not be used.

The Rsq should be  $\geq$ 0.800 and the observation period over which the regression line is estimated should be at least two-fold the resulting  $t_{1/2}$  itself. If these criteria are not met, then the rate constants and all derived parameters (e.g.,  $AUC_{0-\infty}$ ,  $AUC_{extra}$ %, CL/f,  $t_{1/2}$ , and  $V_{z/f}$ .) will be included in the parameter outputs and descriptive statistics but will be flagged and discussed appropriately. Any flags should be included in the study specific SDTM.

For both analytes, if more than 20% of  $AUC_{0-\infty}$  is extrapolated ( $AUC_{extra}\% > 20.0\%$ ), then  $AUC_{0-\infty}$  and  $\lambda_Z$  estimates and parameters derived from them (e.g.,  $CL_f$ ) will be calculated and included in the listing, but flagged as unreliable and set to missing in summaries and in inferential statistical analysis.

The dose amount for investigational medicinal product (IMP) administered is that of the active, free drug substance only, and is synonymous with the measured analyte. No adjustment for the dose amount value of IMP will be applied when 'dose' is used in calculating PK parameters with formulas needing a dose value.

The Phoenix WinNonlin NCA Core Output will be provided in a separate listing.

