The single dose of trial drug administration will occur after 07:00 in the morning of the first day of each period. A total volume of 240 mL water will be consumed with the medication. All subjects will be required to refrain from drinking water during the first 1 hour after drug administration and refrain from eating during the first 4 hours. Standard diet for lunch and dinner will be served. Beverages should be controlled: fluid intake will be controlled for each in-house period for all subjects. The subjects should drink at least 2 L of water during the first 24 hours after drug administration.

Blood Sampling (Postdose)

Blood samples for the determination of bisoprolol and amlodipine will be taken at the specified times (Table 3).

Pharmacokinetic Sampling procedure

For bisoprolol and amlodipine, whole blood samples will be collected in coded, precooled ethylenediamine tetraacetic acid dipotassium salt coated vacutainers by indwelling cannula (short-term peripheral catheter) for the first day and by direct venipuncture for the rest of the time. Blood samples will be kept in an ice water bath pending processing.

For every subject, during each treatment period, a total of 20 samples, approximately 4 mL each whole blood, will be collected at the following times: at predose (Baseline) and at 0.5, 1, 1.5, 2, 3, 4, 6, 8, 10, 12, 15, 24, 36, 48, 72, 96, 120, 144, and 168 hours after dosing. One sample will be collected at End of Trial (Day 29)/Premature Withdrawal. The PK collection time is based on known single-dose PK profiles of both drugs and should be frequent and long enough to characterize the peak and extent of exposure. Plasma samples will be prepared, divided into 2 aliquots and stored at -20 °C.

Subjects who complete both treatment periods will have a total of 41 samples (4 mL whole blood each sample) collected. Total blood volume collection for PK sampling is approximately 164 mL over 5 weeks.

A validated bioanalytical method, using HPLC with MS/MS detection, will be applied to analyze plasma concentration of bisoprolol and amlodipine. The assay and all related procedure will be developed and cross-validated with previously established methods to ensure quality standard and technical specifications are met. Based on previous method, the following criteria are expected:

Analytes: bisoprolol and amlodipine in human plasma

Assay range: bisoprolol 0.500 - 75.000 ng/mL; amlodipine 50.0 - 15000.0 pg/mL

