8.1 Pharmacokinetic Analysis

The following PK parameters will be calculated from plasma concentrations of bisoprolol and amlodipine by applying non-compartmental analysis methods according respective Standard Operating Procedures (SOPs).

C_{max} the maximum plasma concentration observed

t_{max} time of maximum plasma concentration observed

AUC_{0-t} area under the (plasma) concentration-time curve from time 0 to the last sampling time

at which the concentration is at or above the lower limit of quantification, calculated

using mixed log-linear trapezoidal rule

 $AUC_{0-\infty}$ area under the plasma concentration-time curve from time zero to infinity

AUC_{extra} extrapolated part of AUC_{0- ∞} calculated by C_{last}/ λ_z , expressed in percent

 λ_z terminal elimination rate constant

 $t_{1/2}$ half-life

CL/f total clearance following extravascular administration

V_{ss}/f apparent volume of distribution at steady-state after extravascular administration

[figure not shown]
The PK parameter evaluation will be performed using the validated PK software tool Phoenix/WinNonlin.

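### Could the Day 29 pharmacokinetic sample extend amlodipine AUC0-t to 336 h in Period 2 but only 168 h in Period 1?

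*SAP*

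**What the plan says.** Protocol 8.1 runs AUC0-t to the last sampling time "at which the concentration is at or above the lower limit of quantification, calculated" by the mixed trapezoidal rule. SAP 16.3.2 repeats this ("at which the concentration is at or above the LLOQ. Calculated using the mixed log linear trapezoidal rule") and computes parameters on actual elapsed time since dosing. Neither names a latest hour or requires the same end point in both periods.

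Protocol 7.1.3 lists 20 samples per period, from predose to 168 h, and then adds: "One sample will be collected at End of Trial (Day 29)/Premature Withdrawal". The SAP carries the same row in its own schedule (16.3.1: "The PK sampling collection schedule is presented in Table 1 below"), with no period day and no nominal hour. Protocol 5.7 places Day 29 at 14 days after the Day 15 dose.

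Three further rules bear on the question:
- SAP 16.3.1, after allowing exclusion for documented errors or deviations: "Any other PK concentrations that appear implausible to the Pharmacokineticist/PKPD Data Analyst must not be excluded from the analysis".
- SAP 16.3.2, on lambda-z: "The last quantifiable concentration should always be included in the regression analysis".
- SAP 16.3.2, on carry-over: a profile is left out of summaries and inference "if the anomalous predose concentration value is greater than 5.00% of the" Cmax of that profile.

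The expected assay limits are in Protocol 7.1.3: "Assay range: bisoprolol 0.500 - 75.000 ng/mL; amlodipine 50.0 - 15000.0 pg/mL".

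**The concern.** Amlodipine AUC0-t is the endpoint that sets the sample size. If the Day 29 value is at or above the LLOQ and is treated as a Period 2 concentration, the definition as written carries that subject's Period 2 AUC to 336 h, while Period 1 stops at 168 h. The nearest Period 1 counterpart, the Day 15 predose draw, is labelled only as the Period 2 baseline.

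The average extension would go into the period effect. What would remain is that some subjects are extended and others are not, which adds to the residual variance. The margin is thin: printed joint power with 12 subjects is 80.88%. Two analysts could also derive different primary-endpoint values from the same data.

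**Working it through.** **1. The plan's own figure.** Inputs from the Protocol synopsis: ratio 111.22%, within-subject CV 10.4%, limits 80.00% to 125.00%, 90% CI. Exact power of two one-sided tests in a 2×2 crossover uses σ = √ln(1+CV²), SE = σ√(2/n) and n−2 degrees of freedom. Result for amlodipine AUC0-t: 82.13% (n=12), 87.71% (n=14), 91.63% (n=16), as printed in Protocol 8.2.1. The product of the printed powers at n=12 is 1.0000 × 0.9992 × 0.9856 × 0.8213 = 80.88%, also as printed. Joint power therefore reaches 80% when amlodipine AUC0-t power is 0.80/(0.9992 × 0.9856) = 81.2%.

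**2. When is Day 29 quantifiable?** LLOQ is 0.05 ng/mL. The peak is taken at 8 h (assumed, within the 6 to 12 h of Protocol 3.1), with mono-exponential decline over 336 − 8 = 328 h. The documents give no amlodipine Cmax at 5 mg, so 2 to 3 ng/mL is an assumption. The half-life needed is 328 × ln 2 / ln(Cmax/0.05):

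| Cmax (ng/mL) | Half-life needed |
|---|---|
| 2 | 61.6 h |
| 2.5 | 58.1 h |
| 3 | 55.5 h |

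Protocol 3.1 states about 35 to 50 h. At 50 h, the Cmax needed is 0.05 × 2^(328/50) = 4.7 ng/mL. With Cmax 2.5 ng/mL and 50 h, the Day 29 level is 2500 × 2^(−328/50) = 26 pg/mL, about half the LLOQ. Protocol 3.1 also calls elimination biphasic, so applying the terminal half-life all the way from the peak overstates the Day 29 level.

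**3. Size in an affected subject.** AUC0-336/AUC0-168 = (1 − 2^(−336/t))/(1 − 2^(−168/t)) = 1 + 2^(−168/t). This is 1.123 at 55.5 h, 1.151 at 61.6 h and 1.216 at 75.9 h. The last half-life is where 336 h residue reaches 5% of Cmax (328 × ln 2 / ln 20), so the predose rule removes subjects beyond it.

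**4. Effect on the analysis.** Simulated 2×2 crossovers (20,000 per scenario), with the Period 2 AUC extended whenever Day 29 is quantifiable, log-SD of Cmax 0.25, and the 5% predose exclusion applied. All Cmax and half-life distributions are assumed.

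| Median Cmax (ng/mL) | Half-life: median, CV | Quantifiable | CV of AUC0-t | Power n=12 | Power n=16 |
|---|---|---|---|---|---|
| 2 | 40 h, 15% | 0.4% | 10.4% | 82% | 91–92% |
| 2.5 | 45 h, 20% | about 10% | 10.9% | 79% | 90% |
| 3 | 50 h, 25% | 31% | 11.5% | 75% | 87% |

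The mean A/B estimate is 1.112 in every row, so there is no treatment bias. In the last row joint power is 0.9992 × 0.9856 × 0.752 = 74% at n=12 and 0.998 × 0.867 = 87% at n=16.

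**5. Other parameters.** Under mono-exponential decline, lambda-z is the same from either span. The area from 168 to 336 h is (C168 − C336)/λz, so AUC0-168 + C168/λz = AUC0-336 + C336/λz, and AUC0-∞ does not move. Only the extrapolated percentage changes. Bisoprolol falls from 16 to 0.5 ng/mL in five half-lives (50 to 60 h after the peak), so its AUC0-t is untouched, as are both Cmax endpoints.

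**6. Which profile do the documents describe?** Five statements agree:
- The synopsis gives each period eight days of blood sampling.
- Period 2 is Day 15 to Day 22.
- Protocol 7.1.3 gives 20 samples per period, the last at 168 h.
- Protocol Table 4 counts the Day 29 draw under End of Trial, not Period 2.
- In both sampling tables the Day 29 row has no period day and no hour, and it is shared with premature withdrawal, which has no fixed time after dosing.

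**The case for a change.** The strongest argument for a change is that a schedule is not an analysis rule, while the SAP's explicit rules lean towards keeping data. Implausible values stay in, out-of-window samples stay in, and the last quantifiable point always enters the lambda-z fit. The trial is open-label, so the choice is better fixed before concentrations are seen. The assay limits are only expected values. With an assumed LLOQ of 25 pg/mL the half-lives in step 2 fall to 51.9, 49.4 and 47.5 h, the last two inside the stated range. If the median half-life were 60 h with Cmax 3 ng/mL and 25% spread in each, a simulation without the predose exclusion gives power of about 81% (n=16) and 68% (n=12).

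Some of this stands. No sentence caps AUC0-t at 168 h, and the arithmetic is right for its inputs. But the rule on implausible values concerns discarding suspect results, the window rule concerns samples taken late or early, and the lambda-z rule applies within whatever profile is being analysed. None of them assigns the Day 29 draw to Period 2. The larger losses need a median half-life at or above the top of the stated range. With a lower LLOQ more subjects are affected, but each by less: 1 + 2^(−168/47.5) = 1.086.

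**Conclusion.** The wording has a gap, but one that a pharmacokineticist would fill from the schedule: 0 to 168 h in both periods, with the Day 29 value listed only. On that reading the planned power stands at 82.13% and 91.63%.

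On the other reading the effect is essentially nil for half-lives of 35 to 50 h with Cmax up to about 2.5 ng/mL. In the most adverse scenario of step 4 it costs about 5 percentage points of amlodipine AUC0-t power at the planned 16 subjects per cohort. Joint power falls below 80% only near n=12, after all four allowed dropouts, where it starts just 0.88 points above that line. The cost falls on the sponsor as extra variance. The ratio stays unbiased, so a false finding of bioequivalence is not made easier.

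This rests on the expected LLOQ of 50 pg/mL and on assumed values for Cmax and for the spread of half-life, which the documents do not give. A sentence in SAP 16.3.2 would be tidy, but nothing in the conclusion depends on it.

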6.1 Description of the Investigational Medicinal Products

Investigational product:

One tablet of bisoprolol-amlodipine 5 mg/5 mg (as a combination formulation of the 2 active ingredients)

Manufacturer: An appropriate packaging site under the control of Merck; final release will be conducted by a qualified person of Merck

Tablet description: Bispoprolol-amlodipine fixed-dose-combination tablet: equivalent to 5 mg of bisoprolol fumarate and 5 mg of amlodipine per tablet

Comparator-1:

Tablet description: Bisoprolol fumarate (Concor®), light yellow, heart-shaped biconvex film coated tablets, scored on both side

Manufacturer: Bisoprolol; Merck (Darmstadt, Germany) at [name]

Comparator-2:

Tablet description: Amlodipine besylate (Norvasc®), equivalent to 5 mg of amlodipine per tablet; supplied as white, octagonal tablet, scored, debossed on 1 side with "NRV 5" and with "Pfizer" on the opposite side

Manufacturer: Amlodipine; CCI

All trial products will be sourced from respective manufacturer as listed below. A set of in-vitro experiment including dissolution profile and content uniformity are being planned to confirm the dissolution profile of the comparator are within specifications. These in-vitro testing results will be available before the clinical trial conduct.

Bioequivalence Trial of Concor AM[®] vs Bisoprolol and Amlodipine in Chinese Subjects

Drug Treatment	Investigational Product	Comparator-1	Comparator-2
Formulation:	Concor AM [®] Bisoprolol-Amlodipine 5mg/5mg	Concor [®] Bisoprolol 5 mg tablet	Norvasc [®] Amlodipine 5 mg tablet
Manufacturer:	CCI	Merck KGaA., Germany	CCI
Storage Condition	Store in original package; Do not store above 30°C; Protected from light.	Store in original package; Do not store above 25°C; Do not freeze; Protected from light.	Store in original package; Do not store above 25°C; Do not freeze; Protected from light.

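### Protocol 6.1 gives the combination tablet's bisoprolol content as 5 mg of the fumarate salt, but SAP 16.3.2 enters 5 mg as free drug in CL/f and Vz/f and bars any adjustment

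*SAP*

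**What the plan says.** Protocol 6.1 describes the three products.

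- Combination tablet: "equivalent to 5 mg of bisoprolol fumarate and 5 mg of amlodipine per tablet". The salt is named for bisoprolol and the base for amlodipine.
- Comparator-1: "Bisoprolol fumarate (Concor®), light yellow, heart-shaped biconvex film coated tablets". The salt is named, but the description does not say whether the 5 mg strength is salt or free base.
- Comparator-2: "Amlodipine besylate (Norvasc®), equivalent to 5 mg of amlodipine per tablet". Here the substance is a salt and the strength is expressly on the base.

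SAP 16.3.2 sets the dose for the noncompartmental calculations. Under CL/f it says "The dose amounts to be used for this calculation are 5 mg for bisoprolol and 5 mg for amlodipine". Later in the same section it says that the dose "administered is that of the active, free drug substance only, and is synonymous with the measured analyte", and then "No adjustment for the dose amount value of IMP will be applied" wherever a formula needs a dose. That general rule extends the 5 mg to Vz/f.

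The assay section of Protocol 7.1.3 identifies what is measured: "Analytes: bisoprolol and amlodipine in human plasma". The analyte is therefore bisoprolol, not its fumarate. SAP 16.2 lists CL/f and Vz/f among the secondary endpoints, which "will be summarized descriptively by group and treatment on the PK analysis set".

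**The concern.** A clearance or volume is dose divided by a quantity built from analyte concentrations, so dose and concentration must refer to the same chemical entity. The SAP says that they do. Protocol 6.1 says that, for bisoprolol in the combination tablet, they do not. If the protocol is right, following the SAP as written inflates two named secondary endpoints by a fixed factor. Geometric means and their confidence limits would all move together, while CV% and geometric CV% would stay the same. Nothing in the output would reveal the error.

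A further possibility arises because the basis for Comparator-1 is not given. If the two bisoprolol products were labelled on different bases, a shared 5 mg constant would also distort the descriptive comparison of CL/f and Vz/f between treatments.

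**Working it through.** The 5 mg is a definition, so there is no calculated figure in the plan to reproduce. The check is whether the passages agree, and what follows if they do not.

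**Do the passages agree?**

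| Place | Basis of the bisoprolol 5 mg |
|---|---|
| Protocol 6.1, combination tablet | fumarate salt |
| Protocol 6.1, Comparator-1 | not stated (substance named as the fumarate) |
| SAP 16.3.2 | free drug, same entity as the analyte, no adjustment |
| Elsewhere in both documents | bisoprolol 5 mg, basis not stated |

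SAP section 9, which lists changes from the protocol, does not mention the point. The first and third rows conflict for the combination tablet and nothing resolves them. For amlodipine there is no conflict: both descriptions in Protocol 6.1 are on the base.

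**What follows if the 5 mg is salt?**

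Formulas from SAP 16.3.2:

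- CL/f = Dose / AUC0-∞
- Vz/f = Dose / (AUC0-∞ × λz)

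Both are proportional to dose. Let F be the free-base fraction of the labelled 5 mg. The dose that matches the analyte is 5 × F mg. Entering 5 mg instead multiplies both parameters by 5 / (5 × F) = 1/F, an overstatement of 1/F − 1.

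F is not in the documents. Assumed formula weights are 325.45 for bisoprolol and 116.07 for fumaric acid, with two assumed stoichiometries:

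- Two bases per fumarate: F = 650.90 / (650.90 + 116.07) = 650.90 / 766.97 = 0.8487
- One base per fumarate: F = 325.45 / (325.45 + 116.07) = 325.45 / 441.52 = 0.7371

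| Basis of the 5 mg | F | Free base in 5 mg | Overstatement, 1/F − 1 |
|---|---|---|---|
| Free base | 1 | 5.00 mg | 0% |
| Salt, assumed 2:1 | 0.8487 | 4.24 mg | 17.8% |
| Salt, assumed 1:1 | 0.7371 | 3.69 mg | 35.7% |

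**What if the constant is converted when it should not be?**

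If the 5 mg is already free base and is multiplied by F, both parameters are understated by 1 − F: 15.1% with the 2:1 factor and 26.3% with the 1:1 factor. The basis therefore has to be known before the constant is changed.

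**What does not change?**

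AUC0-t, Cmax, AUC0-∞, AUCextra%, tmax, λz and half-life contain no dose term. The four primary endpoints and the bioequivalence decision are untouched. The ratio of CL/f or Vz/f between treatments is also unchanged if both bisoprolol products share one basis, because 1/F cancels.

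**The case against.** The strongest reply is that nothing decision-relevant depends on this. CL/f and Vz/f are only summarized, with no test, threshold or planned comparison against outside values. This stands, and it makes the point a correction worth making rather than a threat to the trial.

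Second, the protocol side is one line of product description, not an analysis instruction, whereas the SAP statement is deliberate. The line may simply be loosely worded. That is possible, but the same section expresses the strength of the amlodipine salt tablet on the base, so the authors did distinguish the two. The SAP's explicitness does not make it correct. It makes the conflict sharper, because the free-drug basis is asserted rather than left open.

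Third, the documents prove a contradiction, not that the SAP constant is wrong. This also stands. Product specifications decide the matter, and they are not in the documents.

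Fourth, the percentages rest on assumed formula weights and stoichiometry, and the range includes zero. They illustrate proportionality and should be read that way.

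Fifth, nothing suggests that Comparator-1 is on a different basis from the combination tablet. Its unstated basis is a gap in description, not a second contradiction. It still needs confirming, since the cancellation between treatments depends on it.

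Finally, the 5 mg is written under CL/f alone. Its use in Vz/f follows from the general no-adjustment rule, which is a fair reading.

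**Conclusion.** The concern holds. Protocol 6.1 and SAP 16.3.2 give incompatible bases for the bisoprolol 5 mg in the combination tablet, and no other text reconciles them. Confidence in the contradiction is high; confidence in any single percentage is not.

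The overstatement of bisoprolol CL/f and Vz/f is 0% if the 5 mg is free base, 17.8% if it is a 2:1 salt and 35.7% if it is a 1:1 salt. The last two figures rest on assumed molecular weights and stoichiometry. Amlodipine is not affected, nor is any endpoint used for bioequivalence. This should be corrected, but it does not put the primary conclusion at risk.

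**What to change.** Reconcile Protocol 6.1 with SAP 16.3.2. Confirm from the product specifications, separately for the combination tablet and Comparator-1, whether the bisoprolol 5 mg is salt or free base, and record the answer in SAP 16.3.2.

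- Where it is salt: use 5 mg × F, with F taken from the specification, as the calculation constant for bisoprolol CL/f and Vz/f. Amend the free-drug and no-adjustment sentences for bisoprolol.
- Where it is free base: keep the SAP constant and correct the wording of Protocol 6.1.

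Keep 5 mg for amlodipine. This concerns only the constant in the pharmacokinetic calculation, not what subjects receive. The cost is one specification check, followed by either one SAP wording change and one constant in the noncompartmental set-up, or one wording correction in the protocol.
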